Proposed radiomic analysis will be as follows: first, gross tumour volume (GTV) delineation will be performed retrospectively by experienced lung malignancy Radiotherapy Oncologists on each patient's images (CT images in DICOM (.dcm) format). DICOM files containing not only the CT images but also the RT structure file will be exported and processed using MODDICOM, an R package developed to optimize automatic loading of DICOM images and radiomic analysis. Radiomic features will then be extracted automatically. The extracted radiomic features belong to different families: Intensity-based, morphological, textural and fractal. All analyzed image features will be based on the standardization criteria of the IBSI initiative.

WP3: omics data modelling, avatar creation and knowledge transfer

Developing accurate predictive models and creating Digital Human Avatars (DHA) - Omics features identification and selection: In the first step, an exploratory analysis across all collected datasets (An estimate of \approx 240 NSCLC patients) will enable the start of the biomarker identification process and restrict the cast amount of information towards a more selected pool of potential biomarkers. This first phase will employ robust data analysis techniques in order to identify relevant variables (T3.1.) in a univariate setting, taking individual statistical distributions, feature-relevant correlations and general descriptive statistics into account.

Patient selection

INCLUSION CRITERIA:

- Patients with (suspected) NSCLC
- Age >18 yrs
- ECOG 0-3
- Written Informed Consent

EXCLUSION CRITERIA:

- ECOG 4
- Psychosocial, or emotional conditions controindicating participation to the study

STATISTICAL ANALYSIS METHODOLOGY

An estimate of 600 Patients (both male and female) with \geq 18 years of age with pathologically proven diagnosis of non-small cell lung cancer (NSCLC) will be enrolled. Sample size was calculated on the basis of G-powerR program for "a priori" analysis, considering α =5% and power of 90%.

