The Wilcoxon Mann-Whitney (WMW) test will be used to investigate the ability of these features to predict clinical outcomes on univariate analysis, and the feature showing the lowest p-value will be considered as the most predictive parameter. Receiver Operating Feature curve analysis (ROC) will also be performed on the most significant feature obtained at WMW analysis, calculating the area under the curve (AUC) with the corresponding 95% confidence interval (CI) according to the Clopper-Pearson method. Model processing will be performed through advanced ML and AI techniques first on a dedicated training dataset to fit the model parameters. The obtained hyperparameters will be tuned on a dedicated validation dataset and finally a test dataset will be employed as a dataset independent of the training dataset but following the same probability distribution.

Predictive model development

The objective of the second phase is creating multiple distinct but modular multivariate models, trained through advanced ML and AI techniques and segmented into specific modular areas of interest (T.3.2).

Different supervised models will be developed including logistic regression, decision tree, support vector machine, random forest, XGBoost classifier, and artificial neural networks. The k-fold cross-validation will be used for hyperparameters tuning. The final step in the proposed methodology is the statistical significance comparison of the performance of the ML models. This will be done evaluating predictive performances in terms of different metrics: the first evaluation will be based on accuracy (number of subjects correctly classified on the total number of patients) while the other will be on precision (true positive on total test positive), recall (sensitivity), F1 score (2*precision*recall/(precision+recall)) and AUC-ROC.

We estimate about 300 NSCLC cases with complete data to start developing the models. Specific care will be taken to always ensure both user friendliness and model explainability as primary pillars of the model development strategies. Easily interpretable values such as SHAP (SHapley Additive exPlanations) values will be attached to each model in order to avoid any black-box approaches that might render model outputs, difficult to explain to the patients during their interactions with the clinicians.

Predictive model validation

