Both the developed model and the comprehensive DHA will be validated in order to test their robustness, transferability and generalizability. Two consecutive validation strategies will be employed respectively: the internal and external validation techniques. We estimate a total number of \approx 420 NSCLC cases to start the validation process. This process will include both internal and external validation. The internal validation step will be focused mainly on techniques such as K-fold cross validation. This will allow to achieve a Transparent Reporting of a multivariable prediction model for Individual Prognosis Or Diagnosis (TRIPOD) level 2b. At this TRIPOD level, data are non-randomly split (e.g., by location or time) into 2 groups: one to develop the prediction model and the remaining dataset to evaluate its predictive performance. In the case of suboptimal performances, all the failing models will be reverted back to the previous stage and the models will be retrained with new specifications in order to increase their robustness. At this point, the models can be validated using external datasets, reaching TRIPOD 3 and 4 levels (External validation). Finally, when the models reach a TRIPOD 4 level, data transferability and full actionability will be granted, allowing the successful and safe application of the model in the clinical Routine (T3.3).

ETHICAL CONSIDERATIONS

Considering the technicality and complexity of the LATERN Project, consortium partners are well aware of the various ethical and legal questions relating to the project. The main ethical issues related to this project include:

the respect for persons and for human dignity; fair distribution of benefits and burden; the rights and interests of the participants; the need to ensure participants' informed consent; processing of personal data; concerns involving the development, deployment and/or use of artificial intelligence (AI)-based systems or techniques.

Protocol LANTERN_v1.0 del 16.12.2022

Therefore, LATERN partners will identify and implement a comprehensive set of ethical and legal requirements in accordance with Declaration of Helsinki principles to ensure compliance for all activities of the project. Appropriate ethical monitoring systems will also be set up.

To this effect, LATERN will implement the following activities:

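### The AUC of the selected feature is given a Clopper-Pearson interval, a binomial method that does not fit an AUC and overstates precision when events are few

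*Combined protocol and SAP*

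**What the plan says.** All references are to the combined protocol and SAP.

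- **WP3** describes the first phase as "an exploratory analysis across all collected datasets", with an estimated 240 NSCLC patients.
- **Statistical Analysis Methodology** screens features by the Wilcoxon-Mann-Whitney (WMW) test: "the feature showing the lowest p-value will be considered as the most predictive parameter". That feature then gets a ROC analysis and an AUC "with the corresponding 95% confidence interval (CI) according to the Clopper-Pearson method". No numerator or denominator is given. The clinical outcome is not defined, and no event share is stated.
- The same section later says that "finally a test dataset will be employed as a dataset independent of the training dataset". That sentence concerns the processing of the models; it does not say that the single-feature AUC is computed there.
- **Predictive model development** lists further metrics, including "accuracy (number of subjects correctly classified on the total number of patients", and AUC-ROC again, without an interval method. It also says: "We estimate about 300 NSCLC cases with complete data to start developing the models".

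No other section gives a method for an AUC interval.

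**The concern.** Clopper-Pearson is exact for x successes in n independent trials. The AUC is the Mann-Whitney statistic divided by the number of event/non-event pairs. Those pairs are not independent, because each patient appears in many of them, and the precision depends on both group sizes. No binomial n reproduces that.

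The likely choice, n = patients, makes an AUC from 24 events and 216 non-events look as precise as one from 120 and 120. This interval is the only uncertainty statement the plan specifies for the feature it calls most predictive. With no denominator named, two analysts could also report materially different intervals from the same data.

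A separate, secondary point is that the feature is chosen by its lowest p-value and its AUC is then computed with no separate data named. The WMW statistic and the AUC are rescalings of each other, so selection on one tends to inflate the other, whatever interval is attached.

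**Working it through.** **Inputs.** From the plan: a 95% interval, about 240 patients at the univariate step (WP3), and about 300 at the start of model development. The plan states no AUC, interval width or event count, so it has no figure of its own to reproduce here. Assumed: a binormal feature, true AUC 0.5 to 0.9, and events in 10% to 50% of patients.

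**Closed form, AUC 0.70, N = 240.** Clopper-Pearson with x = 0.70 × 240 = 168 and n = 240:

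- lower limit = Beta quantile (0.025; 168, 73) = 0.638
- upper limit = Beta quantile (0.975; 169, 72) = 0.757
- width = 0.120, whatever the event share.

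The Hanley-McNeil variance uses both groups (m events, k non-events):

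Var = [A(1−A) + (m−1)(Q₁−A²) + (k−1)(Q₂−A²)] / (mk), with Q₁ = A/(2−A) = 0.5385 and Q₂ = 2A²/(1+A) = 0.5765.

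For m = 24, k = 216: Var = [0.21 + 23 × 0.0485 + 215 × 0.0865] / 5184 = 0.00384. SE = 0.0620 and the 95% width is 3.92 × 0.0620 = 0.243. Clopper-Pearson is 0.120/0.243 = 49% of that.

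The next table adds simulated coverage and DeLong half-widths at true AUC 0.70. The Clopper-Pearson half-width is about 0.060 in every row.

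| Events of 240 | Hanley-McNeil width | Clopper-Pearson width as share | DeLong half-width | Coverage, Clopper-Pearson (n = patients) | Coverage, DeLong |
|---|---|---|---|---|---|
| 24 (10%) | 0.243 | 49% | 0.108 | 71% | 93% |
| 48 (20%) | 0.178 | 67% | 0.082 | 85% | 95% |
| 72 (30%) | 0.152 | 79% | 0.072 | 90% | 95% |
| 96 (40%) | 0.138 | 87% | 0.067 | 92% | 94% |
| 120 (50%) | 0.132 | 91% | 0.066 | 93% | 95% |

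**Coverage over AUC 0.5 to 0.9, N = 240** (5000 replicates per setting, Clopper-Pearson with n = patients):

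| Events | Coverage of the nominal 95% interval |
|---|---|
| 50% | 92-96% |
| 40% | 92-96% |
| 30% | 90-94% |
| 20% | 84-90% |
| 10% | 70-78% |

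Repeat simulations moved the ends of these ranges by one or two points. Over the same settings DeLong covers 90-95% and logit-scale DeLong 92-96%. A stratified percentile bootstrap, run at events 10/30/50% and AUC 0.5/0.7/0.9, covers 91-95%.

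**Does a larger N help?** No. At N = 300 coverage with 10% events is 70-79%. At N = 600 and AUC 0.70 it is 71% with 60 events. The width ratio depends on the event share and hardly at all on N.

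**Other denominator.** With the smaller outcome group as n, coverage at N = 240 is 99-100% and the interval is 1.26 to 2.22 times as wide as DeLong's.

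**Secondary point.** N = 240, all features null, with 20 or 100 candidates assumed: the mean apparent AUC of the chosen feature is 0.58 to 0.67, where the truth is 0.50. Reselecting in each bootstrap sample and evaluating out-of-bag gives 0.49 to 0.51. Evaluating in the same bootstrap sample gives 0.60 to 0.73. A simple optimism correction leaves 0.52 to 0.56.

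**The case against.** The strongest reply is that little hangs on this interval. The step is exploratory, features are ranked by p-value, and models are compared on other metrics and then validated. That is right, and it is why the impact is rated minor.

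Next, the serious under-coverage needs two things the plan does not state: n = patients and few events. With the smaller group as n the error runs the other way. With 30-50% events the shortfall at AUC 0.70 is only about 2 to 5 points, and at AUC 0.90 Clopper-Pearson is as good as plain DeLong or better (93.8/95.9/96.6% against 93.1/94.2/94.8% at 30/40/50% events). This stands as a limit on size. It does not rescue the method, which tracks the AUC's precision under neither denominator, and an uncommon outcome cannot be excluded while the outcome is undefined.

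Plain DeLong has a weak corner of its own, about 90% at AUC 0.90 with 10% events. This is a fair caution, and the reason for the logit-scale option. The plan's 300 belongs to model development, where no Clopper-Pearson interval is specified; it is used here only to show that size does not cure the problem.

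On the secondary point, an all-null simulation is the extreme case. With one truly predictive feature (AUC 0.70) among null ones and 30% events, optimism is only 0.001 to 0.005. This is correct, but it is a favourable case. With one feature at true AUC 0.65, 20 candidates and 10% events, the apparent AUC is 0.668 against a true 0.592 for the chosen feature. With 10 of 100 features at true AUC 0.65 and 30% events, it is 0.708 against 0.650. The size depends on the signal, and the plan gives no ground for assuming the favourable case.

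**Conclusion.** The concern holds. The plan applies a binomial interval to a statistic that is not a binomial proportion, and leaves its denominator open. With n = patients and N = 240, the interval is nearly adequate for balanced groups but covers only 84-90% at 20% events and 70-78% at 10%. With the smaller group as n it is too wide. These figures rest on a binormal feature, true AUC 0.5 to 0.9 and assumed event shares; which case applies cannot be known from the plan.

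The impact is minor, because no decision, model or sample size uses the interval. The rule should still be corrected. The selection optimism is a separate, secondary issue whose size ranges from negligible to about 0.17 on the AUC scale (0.67 against 0.50, all features null).

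**What to change.** In Statistical Analysis Methodology, replace the Clopper-Pearson reference for the AUC with the DeLong method (logit scale if events are few or the AUC is near 1) or a stratified bootstrap. Keep Clopper-Pearson for true proportions on independent test cases, such as accuracy or recall, with the denominator stated.

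For the secondary point, report the selected feature's AUC on the planned test dataset, opened only after feature selection and all models are locked. The locking matters because Predictive model validation allows that "all the failing models will be reverted back to the previous stage" for retraining. Alternatively, repeat the selection inside each bootstrap sample and evaluate the AUC out-of-bag, never in the same sample.

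The cost is a sentence for the interval, a standard software call and no extra patients. Against n = patients the interval usually widens: at AUC 0.70 and N = 240 the half-width goes from 0.060 to 0.066 at 50% events, 0.072 at 30% and 0.108 at 10%. Against the smaller group as n it narrows. Reporting on test or out-of-bag cases will tend to give a less favourable AUC and, with fewer cases, a wider interval.

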samples from all enrolling centres will be stored at the coordinating centre in a dedicated laboratory (**FPG**). In-house samples will be collected immediately after biopsy or surgery, while samples from other RUs will be delivered using an appropriate courier service following standard international rules and laws. A comprehensive molecular characterization and genomic profiling of tumour samples will be performed using the Illumina TruSightTM, which will allow the conversion of DNA and RNA extracted from formalin-fixed paraffin-embedded tissue samples into libraries enriched for cancer-related molecular targets. In our methodological approach, we will assess both DNA and RNA levels using a single high-throughput assay that evaluates a wide range of state-of-the-art clinical biomarkers. Specifically, we will analyze with high fidelity multiple somatic genomic alterations such as low-frequency somatic variants (single nucleotide variants, insertions and deletions, and splice variants) and copy number alterations (CNAs) in identified genes linked to cancer susceptibility and treatment.

WP2: omics data archiving and inter-actionability

The aim of this WP is to allow complete data integration into both existing and new archiving systems (Task 2.1: Data archiving QA), and to ensure an easy and effective omics data inter-actionability (Task 2.2: Interactionability QA). All the considered variables will be recorded according to a shared common ontology based on the variable-specific domains, in order to enhance their direct actionability. A standard unit of measurement will be used in order to record the single variables. Possible discrepancies originated from the use of different scales, will be solved through shared equivalence decision. All the laboratory data used in WP1 (Data A, B, C) will undergo cross quality assurance (QA) procedures among the involved centres prior to data upload in the shared platform. Patient data from **KU**, **DEB** and **HSCSP** will be transferred to **FPG** and **TUD** for the radiomic analysis. The shared general ontology will represent a structured terminological system for data archiving and analysis, granting uniformity and coherence for all the collected variables.

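### Neither the same-distribution test set nor ordinary k-fold cross-validation can show the transferability the plan says it will test, and no held-out centre, period or external dataset is specified

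*Combined protocol and SAP*

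**What the plan says.** All references are to the combined protocol and SAP, version 1.0.

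- **Statistical Analysis Methodology.** Models are fitted on a training set and tuned on a validation set. Finally, "a test dataset will be employed as a dataset independent of the training dataset but following the same probability distribution".
- **Predictive model validation, purpose.** The models and the avatar are to be validated "in order to test their robustness, transferability and generalizability".
- **Predictive model validation, internal step.** This rests mainly on k-fold cross-validation, which is said to allow TRIPOD level 2b. The next sentence describes that level as dividing the data into a development group and an evaluation group on a non-random basis, giving place and time as examples. Models that perform poorly go back and are retrained under changed specifications.
- **Predictive model validation, external step.** "At this point, the models can be validated using external datasets, reaching TRIPOD 3 and 4 levels". A model that reaches level 4 is then regarded as fit for safe use in routine care. The source, size and success criterion of the external datasets are not given.
- **WP3.** Feature selection is described as an exploratory analysis across all the datasets collected, with about 240 patients at its start. Later sections give about 300 cases to start model development and about 420 to start validation. Planned enrolment is 600.
- **WP2.** Patient data from KU, DEB and HSCSP go to FPG and TUD for radiomics. No section sets aside a centre or a calendar period before feature selection.

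**The concern.** A test set drawn from the training distribution measures reproducibility: how well the model does on more patients from the same case mix. Ordinary k-fold measures the same thing, because every fold mixes the same centres and the same period. Transferability asks how the model does where the case mix, scanners, laboratories or outcome rate differ, and neither method poses that question.

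The plan is also at odds with itself. A split by place or time will not in general leave the two parts with the same distribution, so the test set in the statistical section and the level 2b split in the validation section are different objects. K-fold is offered as the route to level 2b but is neither of them.

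Two things are at stake. First, if centres differ in both their feature values and their outcome rates, a model can gain apparent accuracy by recognising the centre. That gain disappears at a hospital it has not seen. Second, permission for clinical use is tied to TRIPOD 4, the least specified step in the plan.

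**Working it through.** **1. The plan's own figures.** Enrolment of 600 cannot be reproduced. "Sample size was calculated on the basis of G-powerR program", with alpha 5% and power 90%, but no effect size or test is given. Solved backwards for two equal groups, two-sided, d = (1.960 + 1.282) × √(2/300) = 0.265. This does not bear on validation and is not pursued.

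The case counts do bear on it:

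- 240/600 = 40%, 300/600 = 50% and 420/600 = 70%.
- If 300 and 420 are separate sets within the 600, then 300 + 420 = 720, and they overlap by at least 720 − 600 = 120.
- If they are cumulative accrual points, 420 − 300 = 120 cases are new when validation starts, and up to 600 − 300 = 300 lie outside the initial development set.

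The counts therefore do not show that no data remain for validation. They show that the allocation is not stated.

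**2. The methods side by side.**

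| Evaluation | Patients tested | Split by place or time? | Can show transfer to a new setting? |
|---|---|---|---|
| Final test set, statistical section | Training distribution | No | No |
| Ordinary k-fold, validation section | Same centres and period as training | No | No |
| Level 2b as the plan describes it | A different place or period | Yes, but none is named | Yes, if kept out of selection and tuning |
| External datasets | Not stated | Not stated | Yes, if identified and unused in development |

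**3. How large the overstatement could be.** The documents give no outcome rate, number of enrolling centres or enrolment per centre, so every input here is an assumption: 300 patients, four centres, 60 features of which 6 carry signal, a ridge classifier, and 200 simulated datasets per setting. Except in the rows with no centre differences, features shift by 0.5 SD between centres. Two signal strengths were used, and setting A was run twice independently. Entries are mean AUC; the last column is pooled 10-fold minus new centre.

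| Setting | Outcome rates by centre | Pooled 10-fold | Leave-one-centre-out | New centre | Difference |
|---|---|---|---|---|---|
| A, run 1 | no centre differences | 0.615 | 0.609 | 0.615 | 0.000 |
| A, run 1 | 20-50% | 0.642 | 0.603 | 0.613 | 0.029 |
| A, run 1 | 15-60% | 0.676 | 0.593 | 0.609 | 0.067 |
| A, run 2 | equal | 0.611 | – | 0.617 | −0.006 |
| A, run 2 | 30-40% | 0.614 | – | 0.616 | −0.002 |
| A, run 2 | 20-50% | 0.641 | 0.601 | 0.613 | 0.028 |
| A, run 2 | 15-60% | 0.678 | 0.595 | 0.607 | 0.071 |
| B, weaker signal | no centre differences | 0.541 | 0.545 | 0.552 | −0.011 |
| B, weaker signal | equal | 0.541 | 0.544 | 0.551 | −0.010 |
| B, weaker signal | 20-50% | 0.585 | 0.542 | 0.551 | 0.034 |
| B, weaker signal | 15-60% | 0.634 | 0.545 | 0.550 | 0.084 |

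The overstatement is 0.03 to 0.08 when outcome rates differ widely and about nil when they are equal or close, even with the feature shifts in place. Leave-one-centre-out falls between 0.005 (0.550 − 0.545) and 0.016 (0.609 − 0.593) below the new-centre value, so its error is small and on the cautious side.

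**4. Precision of a held-out set.** The Hanley-McNeil variance is [A(1−A) + (n1−1)(Q1−A²) + (n0−1)(Q2−A²)]/(n1·n0), with Q1 = A/(2−A) and Q2 = 2A²/(1+A). Assume AUC 0.75 and 30% prevalence. For 150 patients (600/4, assuming four equal centres), n1 = 45, n0 = 105, Q1 = 0.600 and Q2 = 0.643. The variance is (0.188 + 1.650 + 8.357)/4725 = 0.00216, the standard error is 0.0464, and the 95% half-width is 1.96 × 0.0464 = 0.091. By the same formula it is 0.102 for 120 patients and 0.064 for 300.

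**The case against.** A reader might infer that the plan cannot measure transferability at all, that every centre is already inside development, and that nothing is left for the external step. The documents do not support any of these.

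- The validation section itself mentions a split by place or time and a separate external step, so the same-distribution test set is not the only evaluation planned.
- The plan is silent on a held-out centre; it does not rule one out.
- The WP3 phrase about all collected datasets may refer to the omics domains rather than the centres, and it is attached to about 240 of 600 patients.
- External datasets are mentioned, and up to 300 patients may fall outside initial development. An unstated source is not an absent one.
- Storing tumour samples centrally does not show which centres train the model.

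The size is also open to challenge. It needs marked differences in outcome rate, which the documents do not give. The milder gap of 0.03 is smaller than the spread of a 10-fold AUC from one dataset to the next (SD about 0.045). The plan also limits feature differences through IBSI-standardised radiomics, a single genomic assay and cross-centre laboratory checks. These points stand: the figure is conditional.

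Finally, leave-one-centre-out is not the only remedy. Computing the AUC within centre from ordinary 10-fold also removes the inflation: 0.597 against 0.601 for leave-one-centre-out at rates of 20-50%, and 0.591 against 0.595 at 15-60%. That is a useful supplement. But the model has still been trained on patients from each tested centre, so it says nothing about calibration at a centre the model has not seen.

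None of this reconciles the two sections. Ordinary k-fold is still not the split that the plan describes as level 2b.

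**Conclusion.** The concern holds as a mismatch between method and claim, together with an unspecified hold-out. The same-distribution test set and ordinary k-fold support a statement about reproducibility only. The plan's level 2b, its transferability claim and its route to clinical use need a split by place or period, or outside data, and it identifies neither.

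If centres differ in both features and outcome rates, pooled k-fold would overstate AUC at a new centre by about 0.03 to 0.08 under the assumed rates of 20-50% or 15-60% across four centres. If the rates are equal or close, the overstatement is about nil. The textual conflict does not depend on these assumptions. The plan should be changed on this point, since a better method is available within the planned enrolment.

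**What to change.** 1. Reconcile the statistical and validation sections: limit the same-distribution clause to internal validation and state that this step assesses reproducibility.
2. Replace ordinary k-fold, as the evidence for level 2b and transferability, with leave-one-centre-out validation. Repeat feature screening, tuning and fitting without the left-out centre, test on that centre, and rotate. Report AUC and calibration by centre with their spread. Each rotation is a split by location of the kind the plan describes.
3. Refit the final model on all development patients.
4. If a centre or period is to be held out as external, name it before feature selection and keep it out of screening, tuning, training and any retraining after poor performance.
5. State the source and size of any external dataset. Call a result external only if the centre, period or dataset contributed nothing to screening, training or retraining, and do not claim TRIPOD 3 or 4 without one.

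The cost is SAP wording and computing time; items 1 to 3 need no extra patients. The downside is wider intervals by centre (about ±0.09 for 150 patients at the assumed AUC of 0.75 and 30% prevalence) and possibly a lower headline AUC. A centre or period reserved under item 4 would also reduce the number available for development.
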